9.12 Monitoring of renal function

Renal function will be monitored at least weekly throughout the active study drug dosing period. Monitoring will be performed by the research team at each site for all participants, with any reportable AE reporting per the protocol. These research personnel will be blinded. Study drug dose will be adjusted based on the calculated creatinine clearance according to the package insert.

9.13 Monitoring for and managing neutropenia

Suggested Management of Neutropenia. Short-term neutropenia is a potential reportable adverse event of ganciclovir, although the incidence is projected to be low in the ICU setting and was not reported in the phase 2 ICU study.

1. Neutropenia will be monitored at least weekly in all participants while they are in the hospital. Monitoring will be performed by the research team at each site, who will be blinded.
2. If ANC drops below $1000/\text{mm}^3$, study drug will be temporarily held.
3. Concomitant drugs should be reviewed and adjusted as feasible.
4. ANC monitoring should continue (i.e. approximately twice a week without G-CSF; once a week with G-CSF) until the ANC is $> 1000/\text{mm}^3$.
5. A dose of G-CSF may be administered (5 microgram/kg) at the discretion of the treating physician.
6. If the ANC increases $> 1000/\text{mm}^3$ study drug may be resumed.
7. If the neutropenia recurs at levels of $< 1000/\text{mm}^3$, study drug should be discontinued permanently, but the patient should continue to undergo all other study procedures & be followed for safety & other endpoints.
8. If the duration of neutropenia (ANC $< 500/\text{mm}^3$) is ≥ 5 days (with or without G-CSF), the event should be reported as a reportable SAE (see SAE reporting section).

9.14 Pregnancy

Participants who are women of childbearing potential will be advised to use effective contraception during treatment and for at least 30 days following treatment with study drug. Similarly, participants who are men will be advised to practice barrier contraception during and for at least 90 days following treatment with study drug.

If a patient becomes pregnant during the course of the study, no further administration of study drug should be given but other procedures should be completed unless medically contraindicated. The investigator will submit a pregnancy report form to the coordinating center. The Reporting Plan and timeline is described in the table in Section 11.3. If the subject terminates from the study prior to the pregnancy outcome, the site must keep in touch with the patient in order to ascertain the pregnancy outcome. Pregnancy status for all participants who are women of childbearing potential will also be assessed at the Day 28 (in participants who are no longer hospitalized) follow up phone call, and pregnancy within 30 days after the last dose of study drug will be assessed during the Day 180 follow up phone call.

9.15 Unblinding

9.15.1 Unblinding criteria

Unblinding may be precipitated either by conclusion of the study or an emergency situation, in discussion between the site PI and protocol chair(s) (Drs. [name], [name], [name] or [name]). All patients or family members can be informed of their treatment assignment at the conclusion of the study, after all key analyses are complete, and upon written request.

In the event of an emergency situation, patients may be unblinded prematurely. Emergency unblinding decisions will be made by the site PI only after discussion with one of the protocol chairs (Drs. [name], [name], [name] or [name]). Additionally, if a reportable serious adverse event (SAE) occurs which qualifies for expedited reporting to one or more regulatory agencies, the patient's treatment assignment will be unblinded, if specifically requested by the regulatory agencies, the institutional review board (IRB), or the DSMB. All cases of unblinding should be discussed with one of the protocol chairs (Drs. [name], [name], [name] or [name]).

9.15.2 Unblinding procedures

After one of the protocol chairs (Drs. [name], [name], [name] or [name]) agrees with the site PI to unblind the patient's treatment assignment, the protocol chair will request the coordinating site's statistical center (SCHARP) to send a password-protected email to the site PI containing the treatment assignment for the particular patient. The code should not be broken except in an emergency where knowledge of the patient's treatment assignment is absolutely necessary for the further management of the patient, or in the context of review of an expedited reportable adverse event as described in the adverse event section of the protocol. If the treatment assignment is unblinded under any other circumstances, it will be considered a protocol violation. This information should also be recorded in the patient's CRF.

10 LABORATORY PROCEDURES

Routine clinical laboratory tests will be performed through the hospital-based clinical laboratory. In this critically ill population, laboratory tests shall be those deemed necessary based upon clinical indications of the patient; others will be ordered as per protocol.

10.1 Laboratory procedures

Laboratory procedures include but are not limited to:

- Baseline whole blood sample for immunity and biomarker studies.
- ETA at baseline (\pm 1 day of randomization) and then twice weekly (\pm 2 days) while the patient is intubated for CMV viral load, inflammatory biomarkers, characterization of cellular content.
- Aliquot of BALF and/or lung biopsy done for clinical purposes. For patients who undergo lung biopsy or autopsy, a sample of lung tissue (frozen or fresh) is requested.
- Blood samples at baseline, then:
 - Weekly (twice weekly in intensified monitoring subset) until day 28 or hospital discharge, whichever happens first.
 - For CMV viral load, cytokine analysis, and safety labs (CBC with neutrophil count and platelets, and creatinine).
 - Samples for studies to assess CMV-specific immunity and transcriptomics will be collected at selected sites that have the capability for sample processing
- Bacteremia/fungemia and nosocomial pneumonia (including ventilator-associated pneumonia) will be assessed by clinical testing.

10.2 Future use of stored specimens

The investigators intend to store specimens from patients. These samples will be used for future testing and research related to furthering the understanding of CMV and other viral infections and immunologic control, which may require additional IRB approval as specified in the informed consent form. Other testing on specimens will only occur after review and approval by the IRB of the researcher requesting the specimens and at the central IRB at the coordinating site.

10.3 Biohazard containment

As the transmission of CMV and other blood-borne pathogens can occur through contact with contaminated needles, blood, and blood products, appropriate precautions will be employed by all personnel in the drawing of blood and shipping and handling of all specimens for this study, as currently recommended by the CDC and the NIH or other locally appropriate agencies.

All dangerous goods materials, including Biological Substances, Category A or Category B, must be transported according to instructions detailed in the International Air Transport Association (IATA) Dangerous Goods Regulations.

11 ADVERSE EVENT REPORTING

11.1 Reportable Adverse Events

In this trial, we will not collect data on or report every adverse event (AE) by the commonly used standard definition because critically ill patients have innumerable abnormal signs and symptoms associated with their disease that are expected. Similar to other critical care clinical trials, we will utilize a modified definition of reportable AEs.

For this trial, a reportable adverse event is defined as:

1. Any clinically important untoward medical occurrence in a patient receiving study drug or undergoing study procedures which is different from what is expected in the clinical course of a patient with acute respiratory failure/ARDS,

OR,

2. Any clinically important, untoward medical occurrence that is thought to be associated with the study drug or procedures, regardless of the “expectedness” of the event for the course of a patient with acute respiratory failure.

Expected events for patients with acute respiratory failure are clinical occurrences that are perceived by the investigator to occur with reasonable frequency in the day to day care of patients with acute respiratory failure treated in an intensive care unit with respiratory support. Examples of adverse events that are expected in the course of acute respiratory failure include transient hypoxemia, agitation, delirium, nosocomial infections, skin breakdown, and gastrointestinal bleeding. Such events, which are often the focus of prevention efforts as part of usual ICU care, will not be considered reportable adverse events unless the event is considered by the investigator to be associated with the study drug or procedures, or unexpectedly severe or frequent for an individual patient with acute respiratory failure. Examples of unexpectedly frequent adverse events would be repeated episodes of unexplained hypoxemia. This would be in contrast to an isolated episode of transient hypoxemia (e.g. SpO₂ ~85%), related to positioning or suctioning. This latter event would not be considered unexpected by nature, severity or frequency. Expected events for patients with acute respiratory failure will not be or reported in this trial.

The research team at each site will determine if any clinical adverse experiences (while hospitalized) occur during the period from randomization through the last dose of study drug. The site research team will evaluate any changes in laboratory values and physical signs and will determine if the change is clinically important and different from what is expected in the course of patients with acute respiratory failure. If reportable adverse events occur, they will be recorded on the reportable adverse event case report form. All reportable AEs, per the modified definition above, will be graded according to CTC guidelines. The severity of each event should be classified into one of five defined categories as follows:

- Grade 1 Mild
- Grade 2 Moderate
- Grade 3 Severe
- Grade 4 Life Threatening or Disabling
- Grade 5 Death

The Safety and Protocol Adherence Review Team (SPART, see section 14.3) will also review laboratory safety and reportable adverse event data reports monthly. The DSMB will review all reportable AEs during their regularly scheduled meetings.

Note: Study drug specific laboratory events (e.g. hematologic values, renal function) will be collected as secondary safety endpoints.

Note: See additional information outlined in Section 5.4 on definitions of AEs for the purpose of post hoc analyses.

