5. Duration of respiratory support (with Last-Off Approach) among Day 28 survivors, the number of days on any qualifying respiratory support (applying the last-off approach) will be summarized. Participants transferred to LTACHs will be assigned 28 days. Differences between treatment arms will be analyzed using a two-sample parametric t-test. Descriptive statistics (mean, standard deviation, median, quartiles, and range) will also be presented in summary tables.
6. Oxygenation ($\text{PaO}_2/\text{FiO}_2$ ratio) measured daily on study days 1–7 will be visualized using boxplots stratified by treatment arm.
7. ICU-free days, defined as 28 minus the number of days in the intensive care unit (ICU) during the first 28 days post-randomization.
 - Participants who do not survive through day 28 will be assigned zero ICU-free days.
 - Participants who remain in the ICU on day 27 will be assigned zero ICU-free days.
 - Participants who are transferred to LTACH facilities will be assigned zero ICU-free days.
 - Participants who withdraw from the study will be considered as having missing data.Differences in ICU-free days between treatment arms will be analyzed using a two-sample parametric t-test. Descriptive statistics (mean, standard deviation, median, quartiles, and range) will also be presented in summary tables.
8. CMV DNA detection in plasma and endotracheal aspirate (ETA) by day 28 (>0 IU/mL, >1000 IU/mL), defined as positive CMV PCR from ETA, plasma, or serum specimens.
The analysis will be conducted by the unblinded protocol statistician.
Differences in CMV DNA detection in plasma and endotracheal aspirate between treatment arms will be evaluated under the competing risk framework of Fine and Gray (10). Cumulative incidence estimates will be evaluated, and Gray's test p-value will be used to test the difference between arms accounting for death as competing risk.
 - This analysis will include death as a competing risk if it occurs on the same day of the last negative CMV test date.
 - Any CMV reactivation will be considered, even those which were below the level of quantification but greater than 0.
9. A comprehensive list of all reportable AEs of Grade 3 or higher by day 28 will be provided, including onset date, AE verbatim, MedDRA code, SAE/EAE, study day, severity grade, relationship to study drug, outcome, and duration days.

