3.4 Standard dosing regimens

1. Treatment of active CMV infection (i.e. presence of CMV by culture, PCR, or antigen detection).

Dosing of intravenous ganciclovir is 10 mg/kg daily, given as 5 mg/kg every 12 hours (adjusted for renal function). A minimum interval of 6 hours is required between the first and second dose.

2. Prevention of CMV reactivation (in CMV seropositive patients with latent CMV infection but without evidence of active CMV infection)

Dosing of intravenous ganciclovir is 5 mg/kg once daily (adjusted for renal function).

In this protocol we will use an initial 5-day regimen of twice daily dosing intravenous ganciclovir for hospitalized patients, followed by a daily dosing regimen of intravenous ganciclovir. All patients will receive a maximum of 28 days of study drug, provided that they have intravenous access. For patients discharged from the hospital prior to day 28, study drug will be discontinued at the time of hospital discharge or removal of intravenous access, whichever occurs earlier. For patients who remain hospitalized beyond day 28, study drug will be discontinued after day 28. Dose adjustments for reduced renal function will be done according to the package insert.

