3.6.1.1.2 Neutropenia

Neutropenia is the principal toxicity of ganciclovir and valganciclovir. The incidence is highest in HCT recipients and HIV-infected individuals, followed by pediatric patients with congenital CMV disease and solid organ transplant (SOT) recipients. Many studies have demonstrated the effect occurs late after drug administration [56, 61, 62]. In fact, several studies in HCT recipients, the most susceptible population for this complication, show that the median time of onset is 5 weeks after start of drug administration. The most relevant data for the proposed study come from a recent randomized trial of valganciclovir prophylaxis in kidney transplant recipients [56]. In that study, the incidence of neutropenia within 28 days (the duration of treatment proposed in the present study) was only 2%. Another recent randomized trial of valganciclovir vs. ganciclovir at treatment doses (900 mg twice daily and 5 mg/kg twice daily, respectively) for CMV disease in SOT recipients showed a neutropenia rate of 1.2% and 0%, respectively, at 21 days of treatment [57].

Ganciclovir-related neutropenia is reversible [56, 57, 61]. The time to recovery can be hastened by administration of G-CSF [54].

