5.2 Secondary Objectives

The secondary objectives of the study are:

1. To evaluate whether administration of ganciclovir increases VFDs in immunocompetent patients with sepsis-associated acute respiratory failure.
2. To evaluate whether administration of ganciclovir increases total RSFDs (all RSFDs, instead of last-off approach) in immunocompetent patients with sepsis-associated acute respiratory failure
3. To evaluate whether mortality and time to death in the 28 and 180 days is different among ganciclovir recipients relative to placebo recipients, respectively.
4. To evaluate whether duration of mechanical ventilation among survivors in the first 28 days is different among ganciclovir recipients relative to placebo recipients.
5. To evaluate whether duration of respiratory support among survivors in the first 28 days is different among ganciclovir recipients relative to placebo recipients.
6. To evaluate whether oxygenation is different among ganciclovir recipients relative to placebo recipients.
7. To evaluate whether ICU-free days in the first 28 days are different among ganciclovir recipients relative to placebo recipients.
8. To evaluate whether CMV DNA detection in plasma and endotracheal aspirate (ETA) by day 28 is different among ganciclovir recipients relative to placebo recipients.
9. To assess the number and severity of reportable adverse events and reportable serious adverse events in the first 28 days in both groups.

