5.2.1 Secondary Endpoints

1. VFDs (defined to be 28 days minus the duration of mechanical ventilation through day 28 since randomization [a key secondary endpoint]). Participants who do not survive through day 28 are assigned zero VFDs.
2. Total RSFDs (calculated as 28 days minus each day of respiratory support through day 28 since randomization). Participants who do not survive through day 28 are assigned zero respiratory-support-free ventilator-free days.
3. Mortality by day 180 (day 28, day 180, time-to-event).
4. Duration of mechanical ventilation (among survivors) by day 28.
5. Duration of respiratory support (among survivors) by day 28.
6. Oxygenation (PaO₂/FiO₂ ratio) daily on study days 1-7.
7. ICU-free days by day 28.
8. CMV DNA detection in plasma and endotracheal aspirate (ETA) by day 28 (>0 IU/mL, >1000 IU/mL).
9. Number of patients with reportable adverse events of Grade 3 or higher by day 28.

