12.2 Data Collection

Each patient will be assigned an identification number to be used for all patient data. Links to patient name and identifiers will be maintained and stored in files on computers protected by password and in locked office cabinets. Research staff and physicians will remain blinded until the study is completed. De-identified data collected during this study may be used for future research.

Chart abstraction for demographic, laboratory, and physiologic data will occur at study entry, daily on study days 1-7, then twice weekly through day 28 while the patient is hospitalized, and again at hospital discharge or death. While patient remains hospitalized, review of the hospital record will occur daily throughout the hospitalization (to Day 28) to identify any reportable adverse events.

All information will be in Medidata RAVE.

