14.3 Safety and protocol adherence review team

The safety and protocol adherence review team (SPART) will, on a monthly basis, review all clinical and laboratory safety data during the study. The SPART will include CCC PIs (Drs. [name], [name], [name], and [name]), Clinical Site Manager [name], and Clinical Trial Project Manager/Site Monitoring Manager [name]. Meetings of the SPART (by videoconference or teleconference) will occur regularly and will not require attendance of all team members at each meeting. The SPART is responsible for the review of the clinical safety reports, discordant CMV serostatus test results (LFA versus CLIA test), and protocol violations, as well as communication with the IRB, NHLBI executive secretary, and DSMB, as outlined above.

14.4 Data Safety and Monitoring Plan (outlined briefly below and in more detail in Appendix F)

Investigators are responsible for monitoring the safety of patients who have entered this study. While hospitalized, patients will be assessed daily for evaluation of reportable adverse events by the research nurse/coordinator and principal investigator at study sites. Drs. [name], [name], [name] and [name] will act as the investigator on-call for urgent issues and questions; [name] or [name] will serve in this role for any questions about eligible patients at [name] or [name] study sites.

The investigator remains responsible to follow, through an appropriate health care option, reportable adverse events (AEs) that are serious, cause the patient to discontinue before completing the study, or are ongoing at the time of study completion. The site investigators will maintain responsibility for forwarding of reportable SAEs to the coordinating center and local Institutional Review Board. The patient will be followed until the event resolves or stabilizes. Frequency of follow-up is left to the discretion of the investigator.

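### Protocol Section 11.1 ends adverse-event determination at the last dose, which contradicts the day-28 safety endpoint and the protocol's other collection rules

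*Combined protocol and SAP*

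**What the plan says.** Section 11.1 of the protocol is the operative instruction to sites on adverse events. It has the research team determine whether clinical adverse experiences occur while the patient is in hospital, "during the period from randomization through the last dose of study drug".

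The last dose is not a fixed day. Dosing lasts at most 28 days, and under Section 3.4, for patients who leave hospital before then, "study drug will be discontinued at the time of hospital discharge or removal of intravenous access, whichever occurs earlier". Section 9.13 adds permanent discontinuation for recurrent neutropenia.

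The objective and endpoint use a fixed window. Section 5.2, item 9: "To assess the number and severity of reportable adverse events and reportable serious adverse events in the first 28 days in both groups". Section 5.2.1, item 9: "Number of patients with reportable adverse events of Grade 3 or higher by day 28". SAP Section 10, item 9, follows: "A comprehensive list of all reportable AEs of Grade 3 or higher by day 28 will be provided". SAP Section 9 plans frequencies and percentages of patients with each event by arm, but states no window.

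Section 12.2 gives sites a different collection rule from Section 11.1: "review of the hospital record will occur daily throughout the hospitalization (to Day 28) to identify any reportable adverse events".

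**The concern.** The endpoint counts patients with an event by day 28, so every patient should be observed for events over the same period. Section 11.1 instead gives each patient a window that closes on a day fixed after randomization by discharge, loss of intravenous access or discontinuation. Treatment could influence each of these. A site that follows Section 11.1 collects less than the endpoint requires in any patient whose drug stops early, and the final tables would not show which sites did so.

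The harm comparison matters in this trial: SAP Section 4 records that enrollment was closed over safety and futility concerns.

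**Working it through.** The plan gives no figure to reproduce, so the check is a comparison of every place that sets a window for adverse events.

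**Window under Section 11.1 alone.** Let L be the study day of the last dose, with L no later than 28. Determination runs from randomization to day L, and the stretch missing from the endpoint window is 28 − L days. That is zero if L = 28 and positive otherwise. The documents give no distribution of L, overall or by arm.

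**Windows elsewhere in the protocol.**

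| Place | Window for reportable adverse events | Ends at last dose? |
|---|---|---|
| Sections 5.2 and 5.2.1; SAP 10 item 9 | To day 28 | No |
| Section 12.2 | Daily record review in hospital, to day 28 | No |
| Section 14.4 | "While hospitalized, patients will be assessed daily for evaluation of reportable adverse events by the research nurse/coordinator" | No |
| Appendix A | Monitoring row marked at visits through day 28 | No |
| Sections 9.9 and 9.11; Appendix F | Day-28 call after earlier discharge | No |
| Section 11.3 | All reportable events in the study period go on the case report form | No |
| Section 9.13, item 7 | Safety follow-up continues after permanent stop for recurrent neutropenia | No |
| Section 11.1 | In hospital, to last dose | Yes |

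**Who falls between the rules.** There are two groups. Patients still in hospital after their last dose are covered to day 28 by Sections 12.2 and 14.4 and Appendix A, but not by Section 11.1. Patients discharged before day 28 are covered by the day-28 call, but not by Section 11.1. No passage ranks these rules.

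**What the endpoint can lose.** It counts patients, not events. A patient with a qualifying event on or before day L is already counted, and a shorter window cannot remove that patient. A loss requires all of the following:

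- the first Grade 3 or higher reportable event falls after day L and by day 28;
- the site stopped at the last dose, as Section 11.1 says;
- the event was not picked up by the record review, the daily assessment or the call.

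**Whether arms could differ.** Randomization is blocked by site, so sites choosing different rules would affect both arms alike. A difference between arms could arise only through L within sites that applied Section 11.1. Its existence and direction cannot be determined from the documents.

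**The case against.** The strongest reply is that the plan's intent is clear. The objective, endpoint, schedule, record review, daily assessment and day-28 call all point to day 28, and one clause is out of line. That is right, and it limits the point to an inconsistency. It does not remove it, because the clause sits in the section a site would consult on adverse events and nothing overrides it.

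Three stronger readings are tempting, and the documents do not support them.

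- *The trial misses delayed toxicity.* Section 3.6.1.1.2 says of neutropenia: "Many studies have demonstrated the effect occurs late after drug administration". But the median onset it then gives, in transplant recipients, is 5 weeks (35 days), which a day-28 window would also miss. Safety bloods are scheduled on fixed study days while in hospital, not until the last dose, and Section 11.1 itself notes that drug-specific laboratory events are collected separately as secondary safety endpoints.
- *The comparison is biased toward no difference in harm.* A patient stopped for a Grade 3 or higher reportable event is already counted, and neither discontinuation nor discharge is given by arm. Such a bias is possible but not shown.
- *A stated share of the window is lost.* For a stop on day 10 one can write (28 − 10)/28 = 64%. The documents describe no such typical patient, and the figure applies only if Section 11.1 is the sole rule, which it is not.

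It is also fair to say that, with enrollment closed, rewording Section 11.1 cannot change what sites did. The analysis window can still be stated.

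**Conclusion.** The point holds as a contradiction between the site instruction in Section 11.1 and the day-28 safety endpoint with its supporting collection rules. The consequence is possible under-collection of first Grade 3 or higher reportable events between an early last dose and day 28, at any site that followed Section 11.1. The number of patients or events affected cannot be calculated, and no direction of bias is established.

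The verdict rests on reading the Section 11.1 clause literally and on no document ranking the competing rules. If sites worked to Section 12.2 and the schedule, nothing was lost through this clause.

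Some limits would remain under any wording. After discharge, collection rests on one call, which the 4-day window allows as early as day 24, and no study blood is drawn. After withdrawal, safety procedures continue for only 48 hours, although record data are still collected (Section 7.5). Events first appearing after day 28 lie outside the endpoint.

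**What to change.** 1. Amend Section 11.1 so that reportable adverse events are ascertained from randomization through day 28 in every participant, regardless of study drug discontinuation. Use the existing in-hospital record review and, after discharge, the existing day-28 call. Refer to Section 7.5 for withdrawn participants, and make clear how the study-period wording in Section 11.3 relates to this window.
2. State in SAP Section 9 that the adverse-event tables count events through day 28 by arm, in line with SAP Section 10 item 9.
3. Because enrollment is closed, give the medical-record review in Section 5.4 the same window; none is stated there. That review targets effects outside the protocol's definitions, so its findings should be shown separately from the reportable events.
4. As an optional check on size, tabulate last-dose day by arm and the number of reportable events with onset after it by site. Dosing records and onset dates are already planned data (SAP Sections 6.2 and 9).

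The cost is wording and, if wanted, one descriptive table. No visit, sample or contact is added.
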